9.4 Reporting and Exclusions

9.4.1 Evaluation of Toxicity

All patients will be evaluable for toxicity from the time of their first treatment with CB-839 HCl.

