2.4.4 Research Biopsies

After obtaining informed consent, patients with solid tumors will undergo a mandatory tumor biopsy at screening, while optional biopsies are collected only upon patient consent. Patients

who have had a mixed tumor response will have biopsies of two lesions that have had different responses, if deemed safe and possible.

Patients will undergo 3-6 core biopsies mandatory at screening and optional on Week 4 and upon disease progression. An optional FNA core will be collected at screening, Week 4 and upon disease progression. FNA and cores will be used for molecular profiling, including RNA sequencing, DNA sequencing, and RPPA, and PDX generation.

If a patient is having a planned surgery or diagnostic procedure they will not have tumor biopsy. Instead residual tissue from the surgery or diagnostic procedure will be collected.

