5.4 Specimen Collection

5.4.1 Tumor Core Biopsies and Fine-Needle Aspiration

Core needle biopsy (CNB) tumor tissues will be collected for molecular profiling. CNB or fine-needle aspiration (FNA) tumor tissue will be collected for PDX generation. Core biopsies at least 1 cm in length will be obtained through Interventional Radiology by a percutaneous approach using a 16-18-gauge needle; FNA will be obtained for PDX generation, if available. Only percutaneous biopsies will be performed on patients with solid tumors. However, excisional biopsy or endoscopic biopsy is allowed if medically indicated and can be used for analysis.

At each tissue collection time point, at least 5 cores are requested. Each Core should be numbered sequentially in the order in which it was collected.

If four or five cores are obtained, then fix Cores 1 and 2 in formalin, snap-freeze Core 3, suspend Core/FNA 4 in DMEM, and fix Core 5 in formalin. If more than 5 cores can be obtained, fix the additional cores (Cores 6-8) in formalin.

If only three or fewer cores can be obtained, then fix all Cores in formalin.

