9.4.2 Evaluation of Response

All patients who receive at least one dose of study drug are evaluable for response. Patients who are enrolled but who do not receive any study drug may be replaced.

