10.5 Pregnancy

Although not an adverse event in and of itself, pregnancy as well as its outcome must be documented via **CTEP-AERS**. In addition, the ***Pregnancy Information Form*** included within the NCI Guidelines for Adverse Event Reporting Requirements must be completed and submitted to CTEP. Any pregnancy occurring in a patient or patient's partner from the time of consent to 90 days after the last dose of study drug must be reported and then followed for outcome. Newborn infants should be followed until 30 days old. Please see the "NCI Guidelines for Investigators: Adverse Event Reporting Requirements for DCTD (CTEP and CIP) and DCP INDs and IDEs" (at http://ctep.cancer.gov/protocolDevelopment/adverse_effects.htm) for more details on how to report pregnancy and its outcome to CTEP.

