11. STUDY CALENDAR

Cycles	Screening	Cycle 1				Cycle 2				Cycle 3 Onward ¹⁴	EOT	FU/EOS ¹⁵
Days	w/in-28d	1	8	15	22	1	8	15	22	1		Every 3 Months
Window		-3d	± 3d	± 3d	± 3d	± 3d	± 3d	± 3d	± 3d	± 3d	± 3d	± 14d
Informed consent	X											
Demographics	X											
Medical history	X											
Concurrent meds	X	X-----X										
Adverse event evaluation		X-----X										
Physical exam ¹	X	X		X		X		X		X	X	
Performance status (PS) ¹	X	X		X		X		X		X	X	
Vital signs ¹	X	X		X		X		X		X	X	
Weight ¹	X	X		X		X		X		X	X	
Height ¹	X											
Pregnancy Test (B-HCG) ²	X					X				X	X	
Hematology: CBC w/diff, plts ³	X	X	X	X	X	X	X	X	X	X	X	
Coagulation: PT/PTT/INR ¹¹	X				X						X	
Serum chemistry ^{3, 4}	X	X	X	X	X	X	X	X	X	X	X	
Urinalysis ^{3, 5}	X					As clinically indicated						
12-Lead EKG ⁶	X					As clinically indicated						
Radiologic evaluation ⁷ (CT, MRI or PET/ CT)	X									X	X	
Tumor measurements ⁸	X									X	X	
Tumor-specific markers, such as CA19-9, CA-125, CEA, PSA etc. ⁹	X									X	X	
Whole blood for oncometabolomics ¹⁰	X			X	X							
Whole blood for pharmacokinetics (PK) ¹⁰		X		X								
Whole blood for exploratory genetic biomarkers ¹¹	X				X				X		X	
Tumor Biopsy ¹²	X				X						X	
Study Drug: Telaglenastat (CB-839) HCl ¹³		X -----X										
Survival ¹⁴												X

Footnote:

- Physical exam, PS, Vital sign and weight will be performed at Screening, C1-2 D1 and 15, C3 onward D1 and at End of Treatment (EOT). Height will be done at screening.
- Required of all females of child-bearing potential. Screening serum pregnancy test must occur within 3 days prior to C1D1. Urine pregnancy tests will be performed on D1 of every cycle.

3. Does not need to be repeated if the Screening sample was obtained within 3 days prior to C1D1 unless a clinically significant change is indicated.
4. Albumin, alkaline phosphatase, total bilirubin, bicarbonate, BUN, calcium, chloride, creatinine, glucose, LDH, phosphorus, potassium, total protein, SGOT [AST], SGPT [ALT], sodium. Serum chemistry should be determined at the times indicated.
5. All patients with treatment-emergent proteinuria that is $> 2+$ on urine dipstick are required to have a quantitative urine protein evaluation on a random sample and a calculation of the urine protein/urine creatinine ratio. If the results demonstrate nephrotic range proteinuria, a 24-hr total urine protein evaluation should be performed.
6. 12-Lead EKG (single) will be performed at screening and as clinically indicated.

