7. Radiologic evaluation (CT or MRI or PET-CT) will be performed at screening within 28 days prior to C1D1, every 2 cycles (8 weeks), ± 7 days, for the first 13 cycles, then every 3 cycles (12 weeks) ± 7 days and EOT.
8. Tumor measurement: Per RECIST v1.1 for solid tumors and per Modified RECIST (Byrne and Nowak 2004) for pleural mesothelioma. Tumor measurements are repeated every 2 cycles (every 8 weeks) ± 7 days, for the first 13 cycles, then every 3 cycles (12 weeks) ± 7 days and EOT. Documentation (radiologic) must be provided for patients removed from study for progressive disease.
9. Tumor-specific markers, such as CA19-9, CA-125, CEA, PSA, etc. will be tested at the time with radiologic evaluation.
10. Whole blood sample for oncometabolomics and pharmacokinetics will be collected on Day 1 and Day 15 prior to drug administration and after drug administration at 0.5, 1, 2, 4, and 8 hours. In addition, oncometabolomics will be collected on Week 4 (C1D22) post Telaglenastat (CB-839) HCl dose. All "prior to drug administration" samples should be collected after at least 8 hours of fasting (the patient must not eat or drink anything but water). All "after drug administration" samples should be collected after patients are dosed with Telaglenastat (CB-839) HCl immediately after a meal.
11. Optional whole blood sample for exploratory genetic and biomarker testing for cfDNA and WES/RNASeq will be collected at screening, at C1D22, C2D22 and disease progression (EOT) for patients who are consented for such analysis under fasting conditions.
12. Tumor Biopsy: Tumor biopsy at screening are required for all patients for exploratory analyses. In addition, archival tissue samples will be collected if available. Optional on-treatment biopsy will be collected on week 4 (C1D22 ± 3 days) and upon disease progression at EOT. Coagulation tests must be performed and evaluated prior to all biopsy procedures. Patients are consented for tumor biopsy.
13. Telaglenastat (CB-839) HCl dose by mouth twice daily, immediately after a meal on continuous dose from day 1 to day 28-day cycle.
Dosing may occur prior to, during, or after the clinic visit, according to the patient's usual administration schedule.
14. For patients with $\geq SD$ for at least 13 cycles who are on a steady dose for ≥ 2 cycles, study assessments may be reduced to every 3 cycles (i.e., at Cycles 16, 19, 22, etc.) and 3 cycles worth of study medication can be provided at clinic visits.

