12.1.1 Definitions

Evaluable for toxicity. All patients will be evaluable for toxicity from the time of their first treatment with Telaglenastat (CB-839) HCl.

Evaluable for objective response. All patients who receive at least one dose of study drug are evaluable for response. Patients who are enrolled but who do not receive any study drug may be replaced.

Evaluable Non-Target Disease Response. Patients who have lesions present at baseline that are evaluable but do not meet the definitions of measurable disease, have received at least one cycle of therapy, and have had their disease re-evaluated will be considered evaluable for non-target disease. The response assessment is based on the presence, absence, or unequivocal progression of the lesions.

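### The study calendar schedules adverse-event evaluation, and the toxicity set begins, only at first dose, after a screening research biopsy that most patients must have; complications before dosing have no scheduled collection, no procedure attribution and no place in the toxicity tables.

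*Combined protocol and SAP*

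**What the plan says.** **Toxicity set.** Section 9.4.1: "All patients will be evaluable for toxicity from the time of their first treatment with CB-839 HCl". Section 12.1.1 repeats the rule: "All patients will be evaluable for toxicity from the time of their first treatment with Telaglenastat (CB-839) HCl".

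**Calendar.** In Section 11 the row "Adverse event evaluation" has no mark at Screening and runs from Cycle 1 Day 1. The row directly above it, for concurrent medication, does have a Screening mark.

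**Biopsy.** Section 2.4.4: "patients with solid tumors will undergo a mandatory tumor biopsy at screening". It exempts patients with a planned surgery or diagnostic procedure, who give residual tissue instead. Calendar footnote 12 has no such exemption: "Tumor biopsy at screening are required for all patients for exploratory analyses". Section 5.4.1: "Only percutaneous biopsies will be performed on patients with solid tumors". That section specifies a 16-18-gauge needle, requests at least 5 cores, and allows excisional or endoscopic biopsy where medically indicated.

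**Patients never dosed.** Section 9.4.2: "Patients who are enrolled but who do not receive any study drug may be replaced". Section 4.4 allows up to 28 days from registration to treatment, and lets the registration of an untreated patient be canceled.

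**Reporting.** Section 10.3.3 requires any serious adverse event to be reported whether or not it is related, and any on-study death whatever its cause. Its reporting window is defined by its end, 30 days after the last administration. Section 10.4 requires all adverse events in routine data, collected on the trial's schedule, and gives no start date. The five attribution grades in Section 10.2 all refer to study treatment.

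**The concern.** The screening biopsy is done for research. Footnote 12 gives its purpose as exploratory, and the biomarker table in Section 5.7 takes the qualifying mutation from a separate CLIA-certified test. Footnote 12 also requires coagulation tests before every biopsy, so the protocol itself treats the procedure as carrying some risk. That risk falls before the first dose, where the calendar schedules no adverse-event evaluation and the toxicity set has not begun.

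Two things are at stake. Safety is a secondary endpoint, tabulated under Section 9.3 by cohort, type, severity and attribution, and those tables will not show harm from a procedure the protocol mandates. The omission may also be selective: a patient whose complication prevents dosing never enters the toxicity set and may be replaced, while a patient who recovers and is dosed enters it only from that dose. Because the reporting sections give no start point, sites may also handle the same event differently.

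**Working it through.** The plan gives no figure on this point to reproduce. The check has two parts: reading the rules together, and sizing the exposure.

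**1. What happens to a complication between the biopsy and the first dose**

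| Question | Source | Answer |
|---|---|---|
| Is there a scheduled evaluation that would pick it up? | Section 11 calendar | No; the row starts at Cycle 1 Day 1 |
| Is it reportable if serious or fatal? | Section 10.3.3 | It can be read so; no start point is given |
| Is it reportable if non-serious? | Section 10.4 | In principle, but through scheduled collection, and none is scheduled at Screening |
| Can it be attributed to the biopsy? | Section 10.2 | No; all grades refer to study treatment |
| Does it enter the toxicity tables? | Sections 9.4.1, 12.1.1 | No; evaluability begins at first dose |
| If the patient is never dosed? | Section 9.4.2 | Outside the toxicity set; may be replaced |

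The optional Week 4 biopsy falls within scheduled adverse-event evaluation, so the gap concerns the screening biopsy.

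**2. How many patients are exposed**

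Inputs from Sections 9.1 and 9.2: four cohorts, 9 patients in stage 1, 18 more in stage 2, null response rate 0.05, at most 27 per cohort.

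- Probability of stopping after stage 1 under the null: 0.95^9 = 0.630, matching the stated 63%.
- Expected size per cohort under the null: 9 + 18 × (1 − 0.630) = 15.66, matching the stated 15.7.
- Four cohorts: 4 × 15.66 = 62.6, about 63.
- Ceiling: 4 × 27 = 108, as stated.

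These are counts of treated patients. The number biopsied is lower by those exempt under Section 2.4.4 and higher by those biopsied but never dosed. The documents give neither number.

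**3. Chance of at least one complication before dosing**

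The documents give no complication rate, so *p* is an assumption. With *n* patients the expected count is *np* and the chance of at least one is 1 − (1 − *p*)^*n*.

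| Assumed *p* | Expected, *n* = 63 | At least one, *n* = 63 | Expected, *n* = 108 | At least one, *n* = 108 |
|---|---|---|---|---|
| 1% | 0.63 | 47% | 1.08 | 66% |
| 2% | 1.26 | 72% | 2.16 | 89% |
| 5% | 3.15 | 96% | 5.40 | 99.6% |

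For example, at *p* = 0.02 and *n* = 63: 1 − 0.98^63 = 1 − 0.280 = 0.72.

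**The case against.** The strongest reply is that the reporting sections already cover this. Section 10.3.3 requires any serious event, related or not, and any death on study, and sets no first-dose start. Section 10.4 asks for all adverse events. Section 9.4.1 defines who is evaluable, not when data are collected. Section 10.3.1 adds that the full procedures are in NCI guidelines which the protocol only outlines.

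Much of this stands. A reader might infer that adverse events are collected only from the first dose and that biopsy complications fall outside every safety window. The documents do not support that: a serious bleed can be read as reportable, and the start of reporting is undefined rather than set at first dose. Nor do they support the following:

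- **That every patient is biopsied.** Section 2.4.4 exempts some, although footnote 12 says otherwise.
- **That the counts above are uncaptured serious events.** Serious events are the class Section 10.3.3 most plausibly covers, and 108 is a ceiling.
- **That pregnancy reporting shows a contradiction.** Section 10.5 requires pregnancies "from the time of consent to 90 days after the last dose of study drug must be reported", but it also says a pregnancy is not in itself an adverse event. It shows only that the protocol can state a start before dosing when it chooses to.

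The reply does not close the gap. Routine collection follows a schedule with nothing at Screening. The expedited window is framed around the last administration, which gives no clear reference point for a patient never dosed. Even a reported serious event stays outside the toxicity set and has no procedure attribution.

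**Conclusion.** The point holds in a limited form. The start of adverse-event and serious-adverse-event collection is not stated, and the calendar and the first-dose rule leave the period after the screening biopsy uncovered. Three consequences follow from the text:

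- Non-serious complications before dosing have no scheduled collection.
- No complication before dosing, serious or not, enters the toxicity tables or can be attributed to a procedure.
- Patients biopsied but never dosed are outside the toxicity set.

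The size rests on assumed complication rates. Across 1% to 5%, the chance of at least one complication runs from 47% to 96% with about 63 patients and from 66% to 99.6% with 108. These are events at risk of not being captured. How many would actually be lost depends on how sites read Sections 10.3.3 and 10.4, which the documents do not settle. Sample size, type I error and power for the response endpoint are unaffected. This is a cheap improvement to the safety data, not an error in the efficacy design.

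**What to change.** - In Sections 9.4.1, 12.1.1 and 10.4 and in the calendar's adverse-event row, state that collection of adverse and serious adverse events related to protocol-mandated procedures starts at consent or at the screening biopsy.
- In Section 10.2, add an attribution to study procedure beside the attribution to study treatment.
- List procedure-related events before dosing separately, including those in patients never dosed or replaced. Keep first dose as the start for the drug-toxicity tables, so their denominator does not change.
- Reconcile Section 2.4.4 with calendar footnote 12 on who has the screening biopsy, so that the denominator for the new listing is defined.

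The cost is amendment wording, adverse-event entry opened at screening, one extra listing, and a small amount of added screening-period data entry. The case report forms are not part of the documents, so the effort on the forms is an estimate.

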9.4.2 Evaluation of Response

All patients who receive at least one dose of study drug are evaluable for response. Patients who are enrolled but who do not receive any study drug may be replaced.

10. ADVERSE EVENTS: LIST AND REPORTING REQUIREMENTS

Adverse event (AE) monitoring and reporting is a routine part of every clinical trial. The following list of AEs (Section 10.1) and the characteristics of an observed AE (Sections 10.2 and 10.3) will determine whether the event requires expedited reporting via the CTEP Adverse Event

Reporting System (CTEP-AERS) **in addition** to routine reporting.

10.1 Comprehensive Adverse Events and Potential Risks List (CAEPR)

The Comprehensive Adverse Events and Potential Risks list (CAEPR) provides a single list of reported and/or potential adverse events (AE) associated with an agent using a uniform presentation of events by body system. In addition to the comprehensive list, a subset, the Specific Protocol Exceptions to Expedited Reporting (SPEER), appears in a separate column and is identified with bold and italicized text. This subset of AEs (SPEER) is a list of events that are protocol specific exceptions to expedited reporting to NCI (except as noted below). Refer to the 'CTEP, NCI Guidelines: Adverse Event Reporting Requirements' http://ctep.cancer.gov/protocolDevelopment/electronic_applications/docs/aeguidelines.pdf for further clarification. *Frequency is provided based on 161 patients.* Below is the CAEPR for CB-839 HCl (telaglenastat).

NOTE: Report AEs on the SPEER **ONLY IF** they exceed the grade noted in parentheses next to the AE in the SPEER. If this CAEPR is part of a combination protocol using multiple investigational agents and has an AE listed on different SPEERs, use the lower of the grades to determine if expedited reporting is required.

10.1.1 CAEPRs for CTEP IND Agent

10.1.1.1 CAEPR for Telaglenastat (CB-839) HCl (telaglenastat)

Version 2.2, July 21, 2019¹

Adverse Events with Possible Relationship to Telaglenastat (CB-839) HCl (CTCAE 5.0 Term) [n= 161]			Specific Protocol Exceptions to Expedited Reporting (SPEER)
Likely (>20%)	Less Likely (<=20%)	Rare but Serious (<3%)	
BLOOD AND LYMPHATIC SYSTEM DISORDERS			
	Anemia		
EYE DISORDERS			
	Photophobia		
GASTROINTESTINAL DISORDERS			
	Nausea		Nausea (Gr 2)
	Vomiting		
GENERAL DISORDERS AND ADMINISTRATION SITE CONDITIONS			
Fatigue			Fatigue (Gr 2)
INVESTIGATIONS			
	Alanine aminotransferase increased		Alanine aminotransferase increased (Gr 2)
	Alkaline phosphatase increased		
	Aspartate aminotransferase increased		Aspartate aminotransferase increased (Gr 2)
	GGT increased		
	Platelet count decreased		
METABOLISM AND NUTRITION DISORDERS			

Adverse Events with Possible Relationship to Telaglenastat (CB-839) HCl (CTCAE 5.0 Term) [n= 161]			Specific Protocol Exceptions to Expedited Reporting (SPEER)
Likely (>20%)	Less Likely (<=20%)	Rare but Serious (<3%)	
	Anorexia		

¹This table will be updated as the toxicity profile of the agent is revised. Updates will be distributed to all Principal Investigators at the time of revision. The current version can be obtained by contacting [contact]. Your name, the name of the investigator, the protocol and the agent should be included in the e-mail.

Adverse events reported on Telaglenastat (CB-839) HCl trials, but for which there is insufficient evidence to suggest that there was a reasonable possibility that Telaglenastat (CB-839) HCl caused the adverse event:

CARDIAC DISORDERS - Sinus tachycardia

GASTROINTESTINAL DISORDERS - Constipation; Mucositis oral; Oral pain

GENERAL DISORDERS AND ADMINISTRATION SITE CONDITIONS - Death NOS; Fever

INFECTIONS AND INFESTATIONS - Hepatitis viral; Meningitis

INVESTIGATIONS - Blood bilirubin increased; Creatinine increased; Lymphocyte count decreased; Neutrophil count decreased

METABOLISM AND NUTRITION DISORDERS - Hyperglycemia; Hyponatremia; Hypophosphatemia

MUSCULOSKELETAL AND CONNECTIVE TISSUE DISORDERS - Arthralgia; Myositis

NERVOUS SYSTEM DISORDERS - Seizure

RESPIRATORY, THORACIC AND MEDIASTINAL DISORDERS - Dyspnea; Hypoxia

SKIN AND SUBCUTANEOUS TISSUE DISORDERS - Rash maculo-papular

VASCULAR DISORDERS - Hypertension; Hypotension

Note: Telaglenastat (CB-839) HCl in combination with other agents could cause an exacerbation of any adverse event currently known to be caused by the other agent, or the combination may result in events never previously associated with either agent.

10.2 Adverse Event Characteristics

- CTCAE term (AE description) and grade:** The descriptions and grading scales found in the revised NCI Common Terminology Criteria for Adverse Events (CTCAE) version 5.0 will be utilized for AE reporting. All appropriate treatment areas should have access to a copy of the CTCAE version 5.0. A copy of the CTCAE version 5.0 can be downloaded from the CTEP web site http://ctep.cancer.gov/protocolDevelopment/electronic_applications/ctc.htm.

- **For expedited reporting purposes only:**
 - AEs for the agent that are ***bold and italicized*** in the CAEPR (*i.e.*, those listed in the SPEER column, Section 10.1.1) should be reported through CTEP-AERS only if the grade is above the grade provided in the SPEER.
- **Attribution** of the AE:
 - Definite – The AE is *clearly related* to the study treatment.
 - Probable – The AE is *likely related* to the study treatment.
 - Possible – The AE *may be related* to the study treatment.
 - Unlikely – The AE is *doubtfully related* to the study treatment.
 - Unrelated – The AE is *clearly NOT related* to the study treatment.

10.3 Expedited Adverse Event Reporting

10.3.1 CTEP-AERS

Expedited AE reporting for this study must use CTEP-AERS (CTEP Adverse Event Reporting System), accessed via the CTEP Web site (<https://eapps-ctep.nci.nih.gov/ctepaers>). The reporting procedures to be followed are presented in the “NCI Guidelines for Investigators: Adverse Event Reporting Requirements for DCTD (CTEP and CIP) and DCP INDs and IDEs” which can be downloaded from the CTEP Web site (http://ctep.cancer.gov/protocolDevelopment/electronic_applications/adverse_events.htm). These requirements are briefly outlined in the tables below (Section 10.3.3).

In the rare occurrence when Internet connectivity is lost, a 24-hour notification is to be made to CTEP by telephone at [contact]. Once Internet connectivity is restored, the 24-hour notification phoned in must be entered electronically into CTEP-AERS by the original submitter at the site.

